1. FUNDING INFORMATION

1.1 Is your study funded (either directly or through a sub-award) by a Federal Agency (i.e., HHS, NIH, NSF, DOD, DOE, DOJ, or EPA, etc.)?

Yes
 No

1.2 Specifically, is your study funded (or will it be) by the National Institutes of Health (NIH)?

Yes
 No

1.3 Does your study meet the definition of a “Clinical Trial” (see below)?

Yes
 No

HHS and NIH define a **clinical trial** as “a research study in which one or more human subjects are prospectively assigned to one or more interventions (which may include placebo or other control) to evaluate the effects of the interventions on biomedical or behavioral health-related outcomes.”

If your study meets the definition of a **clinical trial**, there are additional requirements that you must follow. Ask your assigned IRB Reviewer or see the [HUA IRB website](#) for more information.

2. RESEARCH COLLABORATIONS AND LOCATIONS

LOCATIONS

Locations refer to the geographic location where the research will take place, not to the people or institutions that you may be collaborating with. Knowing the location helps the IRB determine the local context of the research as well as if there are additional laws, regulations, and policies researchers need to adhere to. If conducting online studies, please indicate the location of the researcher who is hosting.

2.1 Where will this study take place?

- Harvard University
- At another location in Massachusetts
- In another US state (*see below*)
- Internationally (*see below*)

If you chose “in another US state” or “Internationally” describe the laws that will need to be considered:

Technically, students can participate remotely from any location in the world

Please ensure that what you have marked above matches what has been indicated in the ESTR SmartForm, section “Research Locations.”

2.2 Are there any U.S. state laws, international laws, or other laws that the IRB will need to consider when reviewing this study?

- Yes (*see below*)
- No

If “Yes” describe the laws that will need to be considered:

See items in Section 10 regarding Waiver of Parental Consent

2.3 Thinking about the locations where this study will take place, are there any permissions that must be obtained from cooperating institutions, community leaders, government officials? This may include a review by a local ethics board, school district, Ministry of Health, or other institutional approval process, whether domestic or international. A statement that formal review is not required along with your source of information that the proposed research is in accordance with local laws, regulations, and customs is also acceptable.

- Yes (*see below*)
- No

If “Yes” describe and if available, upload any permission documents to the ESTR SmartForm section “Local Site Documents.”

The corresponding Memorandum of Understanding with the Dean of Students Office has been uploaded to ESTR.

2.4 Are there any community or cultural differences for the local population of participants that require consideration? For example, cultural or gender dynamics or social structure considerations.

- Yes (*see below*)
- No

If "Yes" describe:

COLLABORATIONS/SITES

Collaborations, known as "sites" in ESTR, refer to people or institutions that are also taking part in the research study. An important part of knowing about these collaborations is knowing what each person/institution is doing in the research in order to determine the scope of IRB review.

2.5 Will you be collaborating with any researchers not affiliated with Harvard University Area to carry out this study? HMS, HSPH, and HSDM are not part of Harvard University Area.

Yes
 No *(skip to next section)*

2.6 Will the actions of these collaborators include any of the following: Have contact with human subjects; Have access to data that is identifiable; OR Are responsible for the design, conduct, or reporting of the research?

Yes
 No *(skip to next section)*

2.7 Will these collaborators receive their own IRB review?

Yes, all will receive their own IRB review *(skip to next section)*
 No, none will receive their own IRB review
 Some will receive their own IRB review and some will not

2.8 Is another institution and/or researcher requesting that the Harvard University Area IRB act as the IRB of record ("Reviewing IRB") for that institution's or that researcher's activities on the study?

Yes *(Complete the HRP-220: Non-Harvard Personnel Form and attach to the ESTR SmartForm Section "Study Team Members" item 2. Note that those who are considered "volunteers" and are working under the auspice of Harvard University Area will also need to be included in HRP-220)*
 No *(see below)*

If you chose "No" describe the compliance/ethical oversight that this researcher will have in place:

3.3 Are there any other additional study staff whose role in this study requires special qualifications in addition to ethics training (e.g., licensed clinical psychologist, phlebotomist, etc.)?

Yes (see below)

No

If "Yes" describe:

4. RESEARCH PURPOSE

4.1 Provide a brief, non-technical description of the purpose of the research, including the research questions that you hope to answer.

We aim to evaluate the effectiveness of StriveWeekly in preventing symptoms of anxiety and depression within a remote campus learning environment. The use of a waitlist condition will allow us to experimentally assess if the online intervention is responsible for decreasing / preventing worsened anxiety, depression, and stress symptoms over time. Given the previously established effectiveness of StriveWeekly as a universal prevention program, we expect students in the intervention condition to experience significantly better symptoms compared to the waitlist from baseline to posttest.

Alternatively, if the remote campus learning environment and/or the broad pandemic context interferes with the acceptability or effectiveness of StriveWeekly, then we would expect to see no significant differences between the online intervention condition and waitlist condition from baseline to posttest. The results of this project are intended to contribute to generalizable, and publishable knowledge in the field.

Secondary aims include: (a) testing moderators of intervention effectiveness and (b) evaluating the intervention in terms of acceptability (e.g., feedback on program name; demographically representativeness of student user sample; satisfactory adherence and satisfaction rates). Exploratory moderation analyses across groups will help determine whether or not the intervention condition produces unique or additive effects for students with certain characteristics over and above changes demonstrated by similar students in the waitlist condition. Acceptability analyses will allow for more nuanced evaluation of StriveWeekly's effectiveness as a program, beyond its ability to facilitate symptom reduction. Secondary analyses and follow up interviews with diverse subsamples of students will help to assess generalizability of StriveWeekly outcomes, determine acceptability among underserved populations, and inform future research.

4.2 Describe the scientific background, rationale for the study, and importance of this research in adding to existing knowledge.

The burgeoning rise in higher education enrollment continues (Hussar et al., 2020), as young people seek opportunities to further learn, grow, and ultimately increase their chances of a rewarding career, or at least financial security. Although campuses are a place of intellectual pursuit, they are unfortunately also increasingly described as experiencing a “mental health crisis” (Xiao et al., 2017). If campuses are to fully support students, they need to offer effective mental health programming. The ideal mental health services are those that could be offered broadly on campus without further adding to the high demand on counseling centers (Xiao et al., 2017). Given that anxiety and depression are the most commonly reported mental health concerns by students in the United States (American College Health Association, 2020) and internationally (Auerbach et al., 2018), offering universal prevention programming for these concerns can target a large portion of the student population.

In contrast to face-to-face mental health services, online prevention programs offer several benefits for university students, including: convenience of time/location, privacy, ability to be self-reliant, and fewer stigma concerns (Kauer, Mangan, & Sanci, 2014). Reviews have identified many online programs that effectively improve anxiety, depression, and/or stress outcomes through randomized controlled trials with university students (Davies et al., 2014; Farrer et al., 2013; Rith-Najarian, Boustani, et al., 2019), further supporting their promise for dissemination on campuses. Despite online interventions' accessibility, evidenced effectiveness, and potential for large-scale service capacity, most programs tested with university students are of modest scale (i.e., tested with < 200 students; Rith-Najarian, Boustani, et al., 2019). Thus, it is important to offer students online mental health programming that not only has research evidence to support its effectiveness but also its capacity to serve a large number of students.

StriveWeekly has demonstrated broadscale reach and effectiveness in reducing symptoms of anxiety and depression. In earlier implementation studies at the University of California – Los Angeles and at Yale University, StriveWeekly was found to reach hundreds of students with no prior mental health service use (e.g., therapy, psychiatric medication meditation groups, peer counseling; Rith-Najarian, Sun, et al., 2019). Moreover, students from traditionally underserved demographics groups (Asian- and Hispanic/Latinx-identified students) were proportionally represented (Rith-Najarian, Sun, et al., 2019). In a randomized controlled trial of StriveWeekly (ClinicalTrials.gov: NCT04361045), results showed that students assigned to the online intervention experienced small but significant improvements in total symptoms of depression, anxiety, and stress ($d = 0.25$). For students with high baseline motivation for change, intervention effects were even larger ($d = 0.57$). Moreover, symptom improvements were maintained at 3-month follow-up. The quality of the online platform and program content was rated as “good” or “excellent” by 72% of respondents. Only 59% of students initiated using the intervention, but of those students who did the average number of modules with logged skills practice activity was 3.72 (of 8 total).

With the COVID-19 pandemic completely altering the landscape of higher education, students are experiencing more stress than ever. While there has been a full return to in-person instruction for the 2021-2022 academic year, students are still navigating travel restrictions, isolation protocols, and social distancing. Thus, offering an online mental health program such as StriveWeekly will provide students with stress management support regardless of where they are. However, the online intervention's effectiveness has not been tested in the midst of a pandemic or after a remote learning setting. Additionally, the extant literature is limited in the ability to determine to what extent adaptations to therapeutic tools are needed to meet the psychological needs of Sexual and Gender Minority (SGM) individuals. Therefore, in addition to offering StriveWeekly as a service to students, a research trial will be conducted to evaluate the program's effectiveness in addressing anxiety and depression symptoms within this broader unprecedented context. Targeted analyses and follow-up interviews conducted with historically underserved sexual and gender minority students will additionally help support generalizability of StriveWeekly. The results of this trial will support evidence of the effectiveness of offering such online mental health interventions to university students, even when a campus is experiencing unique stressors.

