Data collection. Prior to beginning any research procedures, students will provide their informed consent online via Qualtrics. Participants will be required to login to Qualtrics via HarvardKey Shibboleth, which will be configured to only allow currently active Harvard accounts. Once consent has been obtained for an individual student, they will be directed to an online survey for the study **baseline assessment**. The baseline survey will be open for two weeks. Students assigned to the intervention group will receive an access code in the email, allowing them to access the online platform and set-up their account. The intervention group will then be active for seven weeks, after which the **posttest survey** will open to the intervention group and waitlist group for one-two weeks. There will then be a pause in study activity and data collection from mid-November through winter break. Thereafter, there will be a **2-month follow-up survey** and students who were assigned to the waitlist group will gain access to the online intervention for seven weeks. After this delayed access group completes the intervention, there will be a **5-month follow-up survey** for all participants from both conditions. After the fourth survey, subsets of participants may be invited to additional compensated opportunities to provide further feedback as research data. See timeline table below.

Activity	Timeline
Promotion	August 16 – Sept 6
Recruitment + Baseline Survey	Sept 7 – Sept 17
First Intervention Round	Sept 20 – Nov 7
•Weekly goal-setting & Time management	Sept 20 - 26
•Unhelpful thinking habits	Sept 27 - Oct 3
•Quality time on values & fun	Oct 4 - Oct 10
•Relaxation strategies & Mindfulness	Oct 11 - Oct 17
•Sleep hygiene	Oct 18 - Oct 24
•Physical exercise	Oct 25 - Oct 31

•Wrap-up	Nov 1 - Nov 7
Posttest Survey	Nov 8 – Nov 19
Break	
2-month Follow-up Survey	Jan 24 - Feb 4
Second Intervention Round	Feb 7 – Apr 3
•Weekly goal-setting & Time management	Feb 7 - Feb 13
•Unhelpful thinking habits	Feb 14 - Feb 20
•Quality time on values & fun	Feb 21 - Feb 27
•Relaxation strategies & Mindfulness	Feb 28 - Mar 6
•Sleep hygiene	Mar 7 - Mar 13
Spring break	Mar 14 – Mar 20
•Physical exercise	Mar 21 - Mar 27
•Wrap-up	Mar 28 - Apr 3
5-month Follow-up Survey	Apr 4 - 15
Additional feedback from subgroups TBD	April - May 2022

Conditions

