- o If students under age 18 are prevented from participating in this study due barriers for obtaining parental consent (outlined in responses 3c and 3d above), then some students are unfairly being denied access to a program that is being offered and tested with the support of the Dean of Students Office. This study aims to evaluate how effective the online intervention is for university students during COVID-19 and remote learning, so to functionally preclude some students from enrolling as participants would render findings less generalizable to “all students”.
- If the research involves using identifiable private information or identifiable biospecimens, the research could NOT practicably be carried out without using such information or biospecimens in an identifiable format. (section 9)
 - o All research survey responses will be collected on the Harvard Qualtrics and will include the participant’s official email address. This procedure is necessary in order to link responses from the same participants across all surveys. Other procedures such as asking participants to enter a unique identifier code could risk participants forgetting or mistyping their random identifier, rendering their survey response impossible to link across assessment times.

10.16 Will the parent permission or an agreement to participate process involve obtaining a signature?

- Yes
- No (see below)

If a signature is not obtained, explain why:

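### Protocol 4.1 and 10.15 set the aim in remote learning although 4.2 puts the trial in an in-person pandemic year; the arm comparison can estimate effectiveness there but cannot show whether context changed it, and its interval should reflect the 18 randomised residences

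*Protocol*

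**What the plan says.** **Setting.** Protocol 4.1 opens with the aim: "We aim to evaluate the effectiveness of StriveWeekly in preventing symptoms of anxiety and depression within a remote campus learning environment". Section 10.15, arguing for the waiver of parental permission, repeats that the study is meant to "evaluate how effective the online intervention is for university students during COVID-19 and remote learning". Section 4.2, in the same current text, says "there has been a full return to in-person instruction for the 2021-2022 academic year", while "students are still navigating travel restrictions, isolation protocols, and social distancing". The timeline table in 5.1 runs from a September baseline to subgroup feedback in "April - May 2022", which is that academic year. Section 2.1 adds: "Technically, students can participate remotely from any location in the world".

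**Prediction for a null.** Section 4.1 expects benefit over waitlist. Its one alternative is that remote learning and/or the pandemic "interferes with the acceptability or effectiveness of StriveWeekly", and "then we would expect to see no significant differences between the online intervention condition and waitlist condition from baseline to posttest".

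**Design and analysis.** Section 5.1 randomises residences to immediate or delayed access. The SAP's data analysis paragraph plans piecewise linear mixed models with random intercepts and slopes for participants, and effect sizes (d) from estimated marginal means. It names no residence term and no confidence interval, and leaves moderators to be chosen post hoc.

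**The concern.** Two things in the stated research question do not fit the trial.

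First, the setting. A report that followed 4.1 or 10.15 would claim evidence about a remote campus, when the protocol itself says in-person teaching had resumed.

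Second, the reading of a null. Section 4.1 gives a single reason why the arms might not differ, namely context. The arms differ only in when access is given. No planned contrast varies teaching mode or pandemic exposure, and no context moderator is named. If the result is not significant, the only explanation in the protocol is one that the design cannot examine.

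The SAP compounds this. It names no interval to show how much effect a null leaves open, and its model, as written, ignores the unit of randomisation. An interval from that model would be too narrow if outcomes are correlated within residences.

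**Working it through.** **Step 1: the setting, side by side.**

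| Source | Setting |
|---|---|
| Protocol 4.1, aim | Remote campus learning |
| Protocol 10.15 | COVID-19 and remote learning |
| Protocol 4.2 | In-person teaching resumed for 2021-2022; pandemic restrictions continue |
| Protocol 5.1, timeline | September to May 2022 (dates only) |
| Protocol 2.1 and 5.1 | Individuals may take part remotely |

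The year comes from the timeline and the in-person fact from 4.2 alone. Together they put the trial outside remote learning as the campus setting, but inside the pandemic. Permission for individuals to join remotely does not alter how the campus was taught.

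**Step 2: what the comparison identifies.** Both arms face the same context. The contrast therefore estimates the effect of immediate access within that context, which is a valid estimate of effectiveness there. Whether context changed the effect requires the effect under another context, and the design supplies none.

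**Step 3: rival explanations for a null.** In the earlier trial only 59% started the program (4.2). Section 4.2 also says the program had not been tested during a pandemic, so that low uptake arose without one. The other rival is imprecision, which steps 4 and 5 illustrate.

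**Step 4: inputs.** The documents give no sample size calculation, so there is no figure to reproduce.

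- Clusters (5.1): 7 houses + 2 yards = 9 immediate; 6 houses + 3 yards = 9 delayed. Total 18, so 18 - 2 = 16 df and t(0.975) = 2.120.
- Respondents (11.2): 40 raffle winners at odds of 1:10 to 1:25 imply 40 × 10 = 400 to 40 × 25 = 1,000. With assumed retention of 60% to 100%, n runs from 240 to 1,000. Section 7.1 itself declines to estimate enrolment.
- Earlier effect (4.2): d = 0.25.
- Assumed, not in the documents: two-sided 5% test, equal arms and cluster sizes, baseline-posttest correlation r = 0.6, ICC 0.01 to 0.05.

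**Step 5: formulas and results.** For a difference in change scores in SD units:

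- SE0 = sqrt(2(1 - r) × 4/n)
- DE = 1 + (n/18 - 1) × ICC
- SE = SE0 × sqrt(DE)
- Half-width with residences = 2.120 × SE; without = 1.96 × SE0

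| n | ICC | DE | SE0 | SE | With residences | Without | Ratio |
|---|---|---|---|---|---|---|---|
| 240 | 0.01 | 1.123 | 0.1155 | 0.1224 | 0.259 | 0.226 | 1.15 |
| 240 | 0.05 | 1.617 | 0.1155 | 0.1468 | 0.311 | 0.226 | 1.38 |
| 1,000 | 0.01 | 1.546 | 0.0566 | 0.0703 | 0.149 | 0.111 | 1.34 |
| 1,000 | 0.05 | 3.728 | 0.0566 | 0.1092 | 0.232 | 0.111 | 2.09 |

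Using the noncentral t with 16 df and noncentrality d/SE:

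- A true d of 0.25 (context does no harm) is non-significant in 9% of trials (n = 1,000, ICC 0.01) to 64% (n = 240, ICC 0.05).
- A true d of 0.125 (half the earlier effect) is significant in 13% to 39%.

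On these assumptions, significance alone does not separate an intact effect from a halved one.

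**Step 6: sensitivity to the ICC.** At ICC = 0 and n = 1,000 the half-width is 2.120 × 0.0566 = 0.120 and the ratio is 2.120/1.96 = 1.08. A large trial with negligible clustering could therefore exclude both 0 and 0.25 around an observed 0.125. Imprecision is likely over much of the range but not certain.

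**The case against.** The defence has four fair points.

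- **4.1 is a prediction, not a decision rule.** It says what to expect if context interferes. It does not say that a null proves interference. A reader might infer that converse, but the text does not assert it. This point stands, so the sentence needs qualifying rather than being treated as an error of logic.
- **A positive result is informative.** A reader might infer that, because context is the same in both arms, no result bears on it. That goes too far. Benefit over waitlist would show that the program worked in the 2021-2022 pandemic campus, and would count against context having abolished the effect. It could not show that the effect was undiminished.
- **Much of the right framing is already there.** Section 4.1 also names the pandemic, 4.2 states the gap as testing during a pandemic or after remote learning, and the SAP title refers to COVID-19. In 10.15 the phrase supports a consent waiver, not the analysis. This narrows the conflict to the words on remote learning but does not remove it, since 4.1 is the statement of aim.
- **The missing residence term is a separate SAP matter.** It would be a defect whatever 4.1 said. It belongs here only because the interval is what lets a null be read properly. Section 5.1 does plan a covariate for houses that hold extra events, but that absorbs only the between-residence variation tied to those events.

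The form asks for a lay summary in 4.1, so detailed rules on intervals belong in the SAP.

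**Conclusion.** The point holds in a limited form. The aim in 4.1 and 10.15 conflicts with 4.2 on teaching mode, though not on the pandemic. The randomised comparison remains the right contrast for effectiveness in the actual setting. It cannot show whether that setting changed the effect, and a null cannot be attributed to context. These conclusions rest on the text and the design, not on the arithmetic.

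The figures illustrate how easily a null could arise with no loss of effect: 9% to 64% of trials at d = 0.25, for r = 0.6, n of 240 to 1,000 and ICC of 0.01 to 0.05. A reader might infer that the trial is bound to be too imprecise to tell an intact effect from a halved one. That does not follow, because the documents fix neither sample size nor ICC, and the ICC = 0 case in step 6 is an exception.

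The SAP model as described gives an interval and test that are too narrow for a trial randomised by residence, unless the clustering is negligible.

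**What to change.** 1. **Protocol 4.1 and 10.15:** restate the aim as effectiveness among undergraduates during the pandemic, after the return to in-person instruction, to match 4.2.
2. **Protocol 4.1:** qualify the sentence beginning with Alternatively, so that a non-significant result is not by itself read as interference by context. Label any use of the acceptability analyses, the barrier scale or the COVID-19 life-event items to explore context as exploratory and non-randomised.
3. **SAP:** report the baseline-to-posttest between-group difference with a 95% confidence interval and a test that account for the 18 residences, for example a residence random effect with small-sample degrees of freedom.

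The cost is wording in two protocol sections and one model term. No new data are needed, because residential affiliation is collected at consent (Protocol 9.2). The SAP document is dated 06/01/2023, after the planned end of data collection, but analysis and reporting can still follow these changes. The price is the wider interval shown in step 5, 1.15 to 2.09 times the half-width without a residence term, falling towards 1.08 as the ICC approaches zero.
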